12.2. Device Relationship (Causality)

Causality assessment is required for AEs (and SAEs) that occur during clinical investigations. There is currently no standard international nomenclature to describe the degree of causality or relatedness of an AE with the Investigational Device (ICH, Clinical Safety Data Management: Definitions and Standards for Expedited Reporting, 1994). The following terms will be used during this study:

- Related - An AE that is directly and clearly related to the Investigational Device;
- Possibly Related - There is a reasonable likelihood that the event is due to the Investigational Device, as evidenced by the following:
 - There may be temporal association with the Investigational Device (e.g., within 24 hours of device placement)

- The event, or level of severity of the event, is unlikely to be explained by other etiologies (known to be related to the study disease, subject's baseline medical condition, or concomitant medication)
- Unlikely Related - The AE is not temporally related to the Investigational Device, or is known to be related to one of the following:
 - Morbidity associated with underlying medical condition
 - Anesthesia
 - Upper GI endoscopy
 - Concomitant medication
 - A relationship to the Investigational Device is not biologically plausible
- Not related - The AE is definitely not related to the Investigational Device

12.3. Adverse Event Reporting

12.3.1. Sponsor Reporting Requirements

The Sponsor will conduct an evaluation of any reported UADEs and will report the results of this evaluation to the FDA, IRBs, and participating Investigators within 10 working days after first receiving notice of the event

12.3.2. Clinical Site Reporting Requirements

- All AEs and ADEs will be recorded by the Investigator or designee on the eCRFs provided
- Any SAEs are to be reported to the Sponsor within 36 hours except UADE or suspected UADE which is to be reported within 24 hours of knowledge of the event, followed by a written confirmation by the Investigator within 5 working days
- The Investigator at each site is ultimately responsible for reporting AEs, SAEs and UADEs to the IRB according to local IRB requirements

13. CLINICAL EVENT COMMITTEE

An independent Clinical Events Committee will be formed to review and adjudicate clinical adverse events. The committee will be comprised of physicians who will not participate in the enrollment or treatment of subjects in this study.

Events to be reviewed by this committee will be defined in the CEC charter. Any event listed in the CEC charter that is reported in an eCRF may result in the acquisition of relevant explanatory or supportive documents, which may include source documents from the hospital, as needed. Copies of these documents will be distributed to members of the CEC. The CEC will be blinded to subject's treatment whenever possible. When evaluating the device relationship of an event, the CEC will treat the subject as if he/she is in the treatment group.

The interpretation of the event as classified and adjudicated by the CEC will be used in the final safety analyses.

14. DATA SAFETY MONITORING BOARD

The DSMB is composed of independent physicians and a biostatistician who are not participating in the study and will not be affiliated with BAROnova, the Investigators, or the investigational sites. The DSMB has access to unmasked data, will review the study on a periodic basis, is responsible for making recommendations regarding any safety or compliance issues throughout the course of the study and may recommend to the Steering Committee to modify or stop the study. However, all final decisions regarding study modifications or study termination rest with the Steering Committee.

All cumulative safety data will be reported to the DSMB and reviewed on an ongoing basis throughout enrollment and follow-up periods to ensure subject safety. Every effort will be made to allow the DSMB to conduct an unbiased review of subject safety information. All DSMB reports will be made available to the FDA upon request but will otherwise remain strictly confidential.

DSMB will meet according to the following schedule:

- a. Initial meeting will commence before the study start or shortly after the study start
- b. DSMB will convene as often as necessary but at a minimum twice a year during enrollment phase, with the first review meeting occur within the first six months of enrollment or no later than the first 45 subjects have completed the 1-month follow up visit. If the enrollment dynamic changes, the Sponsor may increase or decrease the frequency of the meeting
- c. DSMB meeting will be convened if the staged safety monitoring threshold has been exceeded as described in Section 5.4 and Section 15.5.6.
- d. Additionally, a DSMB meeting may be requested by DSMB member, the Sponsor, IRB, or the Study Steering Committee at any time to discuss safety concerns if it arises.

In the case that a DSMB meeting is triggered by the staged safety monitoring threshold, the DSMB will review the data and provide recommendation to the Sponsor within 15 days. Based upon DSMB recommendation, Sponsor will implement necessary actions which may range from continuous monitoring, protocol modification, stopping of enrollment to device removal. Sponsor will inform FDA about the course of action following the DSMB review as described in Section 5.4.

15. STATISTICAL DESIGN AND ANALYSIS

15.1. Statistical Overview

Data will be summarized by the number, mean, median, standard deviation and range for continuous variables and by number and relative frequency for categorical variables. Summaries will be presented by treatment group and visit as appropriate. A summary of the subjects combined will be provided for the baseline information only. Missing data imputation approaches are outlined below.

The alpha level will be set to 0.05 based on the two-sided testing and 0.025 for the one-sided approach, if not explicitly stated otherwise. Study success criteria are defined in Section 15.3.1. Statistical testing and confidence intervals for sensitivity analyses and secondary endpoints will be presented as an aid in interpreting study results, but statistical significance is not required for study success. Unless otherwise indicated, all statistical inferences will be based on two-sided 95% confidence intervals and p-values less than or equal to 0.05 will be considered significant.

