15.3. Study Objectives and Hypotheses

15.3.1. Primary Effectiveness Objective

The primary objective of this study is to assess the clinical effectiveness of the BAROnova TransPyloric Shuttle for weight reduction in patients with obesity, with a BMI of 35.0 to 40.0 kg/m², or a BMI of 30.0 through 34.9 kg/m² with one or more obesity-related comorbid conditions over the 12 months treatment period.

The hypothesis associated with the first co-primary endpoint is that the subjects in the Treatment group will have superior weight loss in %TBL compared to subjects in the Control group at 12-month follow up. The statistical null and alternative hypotheses are:

$$H_{i0}: \mu_T - \mu_C \leq \delta \text{ vs.}$$

$$H_{iA}: \mu_T - \mu_C > \delta,$$

Where,

μ_T is the mean % TBL at 12 months in the treated group

μ_C is the mean % TBL in the control group at 12 months.

δ is the superiority margin.

The hypotheses will be tested using a one-sided two-sample t-test for independent samples at the alpha level of 0.025. If the test value exceeds the nominal critical point, the H₀ will be rejected. The testing may be performed using mixed model repeated measurements approach. If the mixed model is used, the decision about the rejection of null hypothesis will be based upon the test for the 12-month follow-up outcomes. The primary statistical test will use $\delta = 0$. If the H₀ is rejected, the 95% confidence interval for the difference in %TBL between the groups will be created. The lower limit of the interval is the statistically achieved superiority margin.

The second co-primary effectiveness endpoint is the percentage of Treatment subjects with a $\geq 5\%$ TBL at 12 months. Proportion of subjects who lose at least 5% of their baseline weight will be compared against the target proportion of 50% using a one-sided test for hypothesized population proportion.

The statistical null and alternative hypotheses are:

$$H_{ii0}: p_T < \Pi_0 \text{ vs.}$$

$$H_{iiA}: p_T \geq \Pi_0,$$

Where,

p_T is the proportion in the study subjects from the Treatment group

Π_0 is the reference proportion (i.e 0.5 (50%))

Study statistical success is achieved if study null hypotheses for both co-primary endpoints are rejected. FDA recommends that the H_{i0} is rejected with superiority margin $\delta = 5\%$ and the H_{ii0} is rejected.

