15.5.4. Secondary Analysis

Secondary endpoints will be summarized by treatment group for the ITT and per-protocol cohorts based on the observed data and include the following summaries:

- Proportion of subjects achieving at least 7% and 10% TBL at 12 months;
- Percent TBL at 1 week, 1, 2, 4, 6, 9 and 12 months in the Treatment versus Control group;
- Percent EWL at 1 week, 1, 2, 4, 6, 9 and 12 months in the Treatment versus Control group;
- Proportion of subjects who achieve at least one obesity class reduction at 1 week, 1, 2, 4, 6, 9 and 12 months in the Treatment versus Control group;
- Change of BMI at 1 week, 1, 2, 4, 6, 9 and 12 months from baseline in the Treatment versus Control group;
- Change in weight-related quality of life at 1 week, 1, 2, 4, 6, 9 and 12 months as assessed by IWQOL-Lite Questionnaire in the Treatment versus Control group;
- Change in eating behavior at 1 week, 1 month and 12 months as assessed by the Eating Inventory;
- Change in appetite, hunger and fullness at 1 week, 1 month, 6 and 12 months as assessed by Visual Analog Scales in the Treatment versus Control group;
- Change in comorbid conditions and selected clinical parameters at 6 and 12 months in the Treatment group:
 - Prevalence of the metabolic syndrome and its individual components
 - Glucose, insulin, and insulin resistance (as estimated by HOMA)
 - High sensitivity C-reactive protein (hsCRP)
 - Lipid levels (LDL-C, HDL-C, and triglycerides)
 - Blood pressure
 - Waist circumference

The analysis of total body weight loss is described above. The other continuous and binary variables will be summarized descriptively by visit with 95% CIs presented for the mean values and proportions, respectively. For continuous endpoints, the change from baseline will be calculated if appropriate, and a t-test or a sign-rank test used to evaluate the null hypothesis that the change from baseline is centered around 0 (no change) within each treatment group. Treatment group comparisons for continuous endpoints will be made using mixed

models with post-hoc tests for each follow-up, and comparisons for qualitative variables will be made using Fisher's exact test, McNemar test or chi-square test, as appropriate.

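### Sections 15.1 and 15.5.4 let any secondary comparison with p of 0.05 or less be called significant, across many visits and scales, with no order, gate or adjustment in the readable text

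*Combined protocol and SAP*

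**What the plan says.** **Success rule.** Section 15.3.1 states: "Study statistical success is achieved if study null hypotheses for both co-primary endpoints are rejected". No secondary endpoint enters that rule. Section 15.1 sets the level of each test: "The alpha level will be set to 0.05 based on the two-sided testing and 0.025 for the one-sided approach".

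**Status of secondaries.** On secondary endpoints and sensitivity analyses, Section 15.1 says that the tests and intervals "will be presented as an aid in interpreting study results, but statistical significance is not required for study success".

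**Significance rule.** The next sentence of 15.1, subject to a proviso that other sections may say otherwise, reads: "all statistical inferences will be based on two-sided 95% confidence intervals and p-values less than or equal to 0.05 will be considered significant".

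**Tests planned.** Section 15.5.4 lists nine groups of secondary endpoints. It compares the arms on continuous endpoints by mixed "models with post-hoc tests for each follow-up", and on proportions by Fisher, McNemar or chi-square tests. The visits differ by endpoint:

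- %TBL, %EWL, obesity-class reduction and BMI change: seven visits each.
- At least 7% and at least 10% TBL: 12 months only.
- Visual analog scales, four visits: "Change in appetite, hunger and fullness at 1 week, 1 month, 6 and 12 months as assessed by Visual Analog Scales".
- Eating Inventory: three visits in 15.5.4 (1 week, 1 month, 12 months). Section 11.5 also collects it at 6 months.
- IWQOL-Lite: seven visits in 15.5.4. Section 11.7 and Appendix B collect it after baseline only at 6 and 12 months, so two comparisons are possible.
- Comorbidity measures: 6 and 12 months, listed for the Treatment group.

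**The concern.** The interpretive-aid sentence settles what counts towards study success. It does not call secondary p-values nominal or exploratory, and the sentence after it gives a verdict of significance at the full per-test level. Nothing readable in 15.5.4 overrides that. The readable text does not order the secondaries, does not make them wait for the co-primaries, and does not say which scale of a multi-scale questionnaire decides.

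A report that follows the plan exactly could therefore call a difference significant at one early visit, on one scale, or after a co-primary has failed. The questionnaires are where this matters most. Section 4 names weight-related quality of life and eating behavior among what the study assesses as secondary endpoints. A device with no effect on them would still have a material chance of showing a significant difference somewhere, and the plan gives the reader no means of telling that apart from a real effect.

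**Working it through.** **The plan's own figures.** The only error rate stated for these tests is the per-test level, 0.05 two-sided. No family-wise figure is given for the secondaries, so there is none to reproduce. The Section 15.4 power does reproduce: with 162 and 81 subjects, difference 8, SD 9 and margin 4, the standard error is 9 × √(1/162 + 1/81) = 1.225. Power is then Φ(4/1.225 − 1.96) = Φ(1.31) = 0.90, as stated. It matters here because, under the planning assumption of 13% against 5%, the 12-month %TBL null is false. The check therefore uses the questionnaires, whose nulls can be true even if weight falls.

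**Step 1: count the questionnaire comparisons.** Assumptions: one IWQOL-Lite total score; the three Eating Inventory dimensions named in Section 11.5; three VAS dimensions (appetite, hunger, fullness); each compared between arms under the general sentence in 15.5.4.

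- At 12 months only: 1 + 3 + 3 = 7.
- All visits both listed and collected: IWQOL-Lite 1 × 2 = 2, Eating Inventory 3 × 3 = 9, VAS 3 × 4 = 12; total 23.

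**Step 2: independent tests, as an upper reference.** 1 − 0.95^7 = 0.302; 1 − 0.95^23 = 0.693.

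**Step 3: correlated tests.** The documents give no correlations, so a common correlation ρ from 0.2 to 0.8 is assumed. With k normal test statistics, all nulls true and c = 1.96:

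P(at least one) = 1 − ∫ [Φ((c − √ρ z)/√(1−ρ)) − Φ((−c − √ρ z)/√(1−ρ))]^k φ(z) dz

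For false results favouring the device, the second Φ term is dropped.

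| Tests | Direction | ρ = 0.2 | ρ = 0.5 | ρ = 0.8 |
|---|---|---|---|---|
| 7 | either | 28.7% | 23.0% | 14.9% |
| 7 | favours device | 14.7% | 11.5% | 7.4% |
| 23 | either | 63.6% | 44.9% | 23.5% |
| 23 | favours device | 34.6% | 22.5% | 11.8% |

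**Step 4: a different correlation structure.** A simulation let correlation fall with distance between visits (0.7 to 0.9 for adjacent visits) and set it at 0.3 to 0.6 between scores. It gave 41% to 61% for the 23 tests. With one score per questionnaire (2 + 3 + 4 = 9 tests) it gave 24% to 33%.

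**Not counted.** Within-group tests, comorbidity tests and the parallel ITT and per-protocol analyses are left out; each adds further p-values.

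**The case against.** The strongest reply is that the plan already puts these tests in their place. Section 15.1 makes them interpretive, 15.3.1 ties success to the co-primaries alone, and 15.5.4 speaks largely of descriptive summaries. No secondary claim is defined, so harm arises only if nominal results are later presented as findings. This stands as far as study-level type I error goes, which is unaffected. It does not remove the significance wording, which is part of the plan.

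Four stronger readings are tempting but not supported:

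- **That a false secondary claim is likely.** Counting every between-arm secondary test gives about 52: the 23 above, 2 responder proportions, 6 %TBL visits before 12 months, and 7 each for %EWL, obesity class and BMI (23 + 2 + 6 + 21). At ρ = 0.5 the chance is 63%, but only if every weight-based null is true, contrary to the plan's own assumption. Those endpoints also derive from the same weights and are strongly correlated; at ρ = 0.8 the figure is 30%.
- **That a promised 5% is exceeded.** The 5% is a per-test level. The plan promises no family-wise rate for the secondaries.
- **That no secondary has a deciding visit.** Section 6.2 fixes the 7% and 10% TBL proportions and the obesity-class reduction at 12 months, although 15.5.4 then lists obesity class at seven visits.
- **That every secondary is tested at seven visits.** Only the four weight-based endpoints can be.

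The absence of adjustment is shown only for the readable text. Section 14 links 15.5.6 to staged safety monitoring; what 15.5.7 contains is not known.

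**Conclusion.** The point holds as a gap in labelling and multiplicity control for the secondary endpoints, not as a flaw in the primary decision. If the questionnaire nulls are true, following the plan as written gives about a 15% to 29% chance of at least one nominally significant questionnaire difference at 12 months (7 tests). Across visits (23 tests) it is about 24% to 64%. Roughly half of these chances apply to results favouring the device.

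The sizes rest on assumed correlations of 0.2 to 0.8 and on the assumed number of scores per questionnaire. They show a substantial chance of a misleading label, but not that one is more likely than not across the whole range. Study success, primary power and sample size do not change.

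**What to change.** **Section 15.1.** Limit the significance sentence to the two co-primary tests, at one-sided 0.025, and to any secondary endpoints in a pre-specified ordered list.

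**Section 15.5.4.** Add wording to this effect: If both co-primary null hypotheses are rejected, the listed 12-month Treatment versus Control comparisons are tested in fixed order, each at two-sided 0.05, stopping at the first non-significant result. All other secondary endpoints, visits and scales are reported with estimates, 95% confidence intervals and nominal p-values, without a statement of significance.

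The sponsor chooses the content and order of the list before unblinding, naming one score for any multi-scale questionnaire it includes. The fixed sequence holds the chance of any false significant result within the list at 5% or less. If no secondary claims are wanted, no list is needed: one sentence labelling all secondary p-values nominal is enough. The IWQOL-Lite and Eating Inventory visits in 15.5.4 should be reconciled with the collection schedule in the same edit.

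**Cost.** A few sentences of wording. No new data, no more subjects, and no change to the primary tests or their power. The downside is that endpoints off the list, or placed after one that fails, cannot be called significant.

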15.2. Analysis Populations

The following analysis populations are defined for the study: Intent-to-Treat (ITT), modified Intent-to-Treat (mITT), Per-Protocol (PP) and Completed Cases (CC). The primary effectiveness hypotheses will be tested on the PP population. The primary safety analysis will be performed on mITT population. The ITT and CC populations will be used in a sensitivity analysis of the primary effectiveness endpoint.

- Intent-to-Treat: The Intent-to-Treat population includes all randomized and enrolled subjects as defined in Section 7.4 regardless of whether or not the subject received the randomized treatment.
- Per-Protocol: The Per-Protocol population is a subset of the ITT population and includes all subjects who receive the assigned treatment and do not have any major eligibility violations.

- **Modified Intent-to-Treat:** The mITT population consists of the ITT population subjects who received the assigned treatment and that have at least one post-treatment follow-up, including the index procedure visit.
- **Completed Cases:** The CC population includes all enrolled subjects who have the 12-month follow-up visit, or have completed the study based on reaching the BMI objective of $\leq 22 \text{ kg} / \text{m}^2$ in two consecutive follow-up visits as described in Section 5.1.

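### Both co-primary tests run on the Per-Protocol set, which failed TPS delivery can shrink in the Treatment arm only; ITT cannot change the success decision and is not all randomised subjects

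*Combined protocol and SAP*

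**What the plan says.** Section 15.2 names the deciding set: "The primary effectiveness hypotheses will be tested on the PP population". PP is a subset of ITT and "includes all subjects who receive the assigned treatment and do not have any major eligibility violations". ITT "includes all randomized and enrolled subjects as defined in Section 7.4". Its role is limited: "The ITT and CC populations will be used in a sensitivity analysis of the primary effectiveness endpoint". Section 15.5.3 repeats this.

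Section 15.1 says of sensitivity analyses and secondary endpoints that results are shown as an aid, "but statistical significance is not required for study success". Section 15.3.1 gives the success rule: "Study statistical success is achieved if study null hypotheses for both co-primary endpoints are rejected". The first co-primary is tested at margin 0. If it is rejected, a 95% confidence interval follows: "The lower limit of the interval is the statistically achieved superiority margin". The section also notes: "FDA recommends that the H_{i0} is rejected with superiority margin" of 5%.

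Three procedural sections matter as well:

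- Sections 5.2 and 11.9.3 place randomisation after the screening endoscopy and before the Access Sheath. Section 11.9.3 defines the sham as anaesthesia plus the sheath, without a TPS.
- Section 7.4 makes a subject enrolled only when the sheath has been introduced.
- Section 7.5 ties retention in follow-up to being enrolled.

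**The concern.** There are two defects.

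**The deciding set is formed after randomisation, by a step that exists in one arm only.** A sheathed Control has already received the assigned treatment. A sheathed Treatment subject can still fail TPS delivery and then leaves PP. ITT keeps that subject, but a contrary ITT result could not change the success decision. Section 5.3 forms the Treatment group by randomisation and Section 6.1 defines co-primary 2 on that group, yet success is judged on a later subset of it.

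**ITT is not all randomised subjects.** Someone randomised but never sheathed, in either arm, is not enrolled and so is outside ITT. PP and mITT are subsets of ITT, and Completed Cases also requires enrolment, so that person is in none of the four sets. Nothing secures a 12-month weight for them. Even the sensitivity analysis therefore cannot recover the full randomised comparison.

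At stake are the margin reported for co-primary 1 and the false-success rate of co-primary 2. Co-primary 2 is a one-group test against 50%, so removing poor responders raises the observed rate directly.

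PP is not a completers set. Dropouts and early removals stay in it and are multiply imputed under Section 15.5.3.

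**Working it through.** **Inputs.** From Section 15.4: means 13% and 5% (difference 8), SD 9 (alternative 7), 162 Treatment and 81 Control, 65% responders assumed. From Section 15.3.1: one-sided 0.025 t-test and a 50% target; Section 15.1 sets 0.025 for one-sided tests generally. From Section 3.4.3: 20 of 20 deliveries with the second-generation device, so the exact 95% upper limit for failure is 1 − 0.025^(1/20) = 16.8%. This trial uses the third generation (Section 3). No failure rate f is given for it, so f = 2%, 5% and 10% are assumed.

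**The plan's own figures.** Noncentral t power at 162/81 is 90.2% (margin 4) and 68.4% (margin 5) with SD 9, and 98.7% and 88.0% with SD 7. These agree with Section 15.4.

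**Co-primary 1.** Undelivered subjects are given the 5% Control mean. The all-randomised difference is 8(1 − f). The expected lower 95% limit is difference − t × 9 × √(1/n + 1/81), with n = 162(1 − f) rounded in PP and n = 162 in all randomised. At f = 0 it is 5.59.

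| f | PP n | Difference, all randomised | Lower limit, PP | Lower limit, all randomised |
|---|---|---|---|---|
| 2% | 159 | 7.84 | 5.58 | 5.43 |
| 5% | 154 | 7.60 | 5.57 | 5.19 |
| 10% | 146 | 7.20 | 5.54 | 4.79 |

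The two sets fall on opposite sides of 5 only at 10% failure. Margin-0 power is at least 0.9999 in all randomised.

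Now suppose the true all-randomised difference is exactly 5. The PP difference is 5/(1 − f) = 5.10, 5.26, 5.56. PP then rejects the 5-point margin 3.0%, 4.0% and 6.5% of the time with SD 9 (3.2%, 4.6%, 8.2% with SD 7), against a nominal 2.5%.

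**Co-primary 2.** Let r be the share of undelivered subjects who reach 5% TBL. With a true all-randomised rate of 50%, the PP rate is (0.5 − f·r)/(1 − f). Exact critical counts are 93 of 159, 90 of 154 and 86 of 146. With no exclusions (94 of 162) the size is 2.46%.

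If weight loss is normal, a mean of 5% gives r = 0.50. A mean of 3.5%, the one-year result of the brief-counselling arm described in Section 2.3.1 (from which Section 8 says this lifestyle programme is adapted), gives r = 0.434 with SD 9.

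| r | f = 2% | f = 5% | f = 10% |
|---|---|---|---|
| 0.50 | 1.9% | 2.2% | 1.9% |
| 0.434 | 2.1% | 2.7% | 2.9% |
| 0.40 | 2.2% | 3.0% | 3.6% |
| 0.25 | 2.6% | 4.5% | 8.0% |
| 0 (worst case) | 3.5% | 8.6% | 23% |

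**How few subjects can reverse a result.** With 180 Treatment subjects, two of them undelivered non-responders, PP passes at 103/178 (exact p = 0.021) and the full group fails at 103/180 (p = 0.031; 104 needed).

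**The case against.** The strongest reply is that the success decision is intact on the plan's own assumptions. Co-primary 1 is tested at margin 0 and cannot realistically change. If undelivered subjects behave like Controls at the planned 5% mean, half respond and co-primary 2 shows no inflation. The inflation figures also assume a true rate of exactly 50%. At the planned 65% among recipients (n = 162), the chance that PP passes while all randomised fails is about 0.2% at 2% failure and 1.0% at 5% failure with r = 0.5, and about 0.3% and 1.5% with r = 0.434. All of this stands, and it limits the weight of the point.

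Delivery failure may also be rare. It did not occur in 20 feasibility subjects, and Section 16.2.1 provides training and in-person support for at least the first five procedures per site. That is fair, but the 20 subjects had an earlier device and the upper limit is 16.8%.

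The 5-point margin is an FDA recommendation, not part of the stated success rule, so 3.0% to 6.5% is not the trial's type I error. That is correct. It is the error of a claim the plan prepares by reporting the achieved margin.

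Section 15.3.1 describes the Treatment mean as that of the treated group, and Section 6.1 times the endpoints from the index procedure. This wording leans towards treated subjects, but it neither justifies PP nor gives ITT any weight in the decision.

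ITT results will be reported, so a divergence would be seen. It would still not count. Finally, no figure above measures the unsheathed subjects. That group may be very small, since randomisation and sheath placement fall within one procedure.

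**Conclusion.** The concern holds and should be fixed. Both co-primaries are decided on a post-randomisation subset that failed TPS delivery can reduce in the Treatment arm only. ITT has no say in success and itself leaves out randomised subjects without a sheath.

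The size is modest under the planning values. The margin-0 decision does not move, and the achieved margin drops below 5 only at 10% failure. Co-primary 2 error rises only if fewer than half of the undelivered subjects respond. It becomes material when failure is around 5% to 10% and a quarter or fewer respond. These sizes rest on assumed failure rates, Control-like mean loss without a device (co-primary 1) and assumed responder shares (co-primary 2). The structural defect rests on the plan's definitions alone.

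**What to change.** - **Section 15.2 and the Section 1 summary:** define ITT as all randomised subjects, analysed as randomised. Remove the enrolment condition and, in 15.2, the reference to Section 7.4.
- **Section 15.2:** test both co-primaries on ITT and make PP and CC supportive. Change the sensitivity sentences in 15.2 and 15.5.3 from ITT and CC to PP and CC.
- **Section 7.5:** ask randomised subjects without a sheath or TPS for a 12-month weight. For sheathed subjects this only confirms that existing follow-up continues.
- **Section 15.5.3:** keep multiple imputation as the single primary missing-data rule. Add that a missing weight of a Treatment subject without a TPS is imputed from Control-group data, not as if a device were in place. Counting such subjects as non-responders belongs in a sensitivity analysis only.

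**Cost.** Wording in four places, a few extra weights, and a slightly smaller expected effect. Power at 162/81, with SD held constant (mixing in undelivered subjects would lower it slightly further):

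| Test on all randomised | f = 0 | 2% | 5% | 10% |
|---|---|---|---|---|
| Margin 5, SD 9 | 68.4% | 64% | 56% | 43% |
| Margin 5, SD 7 | 88% | 84% | 78% | 63% |
| Co-primary 2, r = 0.5 | 97% | 97% | 96% | 94% |
| Co-primary 2, r = 0 | 97% | 94% | 85% | 58% |

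The co-primary 2 rows use a rate of 0.65(1 − f) + f·r. PP would keep 68%, 68% and 67% at margin 5 with SD 9. Margin-0 power stays above 99.9% throughout.
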